6.5 POOLING OF CENTRES

This section is not applicable because centre/country is not included in the statistical model.

6.6 HANDLING OF MISSING DATA AND OUTLIERS

All patients will be followed to collect necessary efficacy and safety information, even if patients discontinue study medication prematurely.

Missing data will not be imputed in general. Specification regarding missing thrombus assessment is specified in [Section 7.4](#).

For missing or incomplete AE dates, BI internal procedures and guidelines will be followed [\(1\)](#). Handling of missing PK/PD data will be performed according to the BI standard procedures [\(2\)](#).

6.7 BASELINE, TIME WINDOWS AND CALCULATED VISITS

Baseline values will be the last available measurements taken prior to first administration of DE or SOC (same dates are allowed).

7. PLANNED ANALYSIS

Descriptive statistics for continuous variables will be N (number of patients with non-missing values), mean, standard deviation (SD), minimum, median, and maximum. In general, means, medians, SDs, will be presented to one more decimal place than the raw data. Minimums and maximums will be presented to the same number of decimal places as the raw data.

Geometric means and geometric coefficients of variation will be used in summaries of PK concentration values.

Tabulation of frequencies for categorical data will include all possible categories, unless otherwise specified (e.g. adverse event terms) and will display the number of observations in a category as well as the percentage (%) relative to the respective treatment group.

Percentages will be rounded to one decimal place. A missing category will be displayed if and only if there are actually missing values. Percentages will be based on all patients in the respective patient set whether they have non-missing values or not.

7.1 DEMOGRAPHIC AND OTHER BASELINE CHARACTERISTICS

Descriptive statistics will be provided for demographics and baseline disease characteristics. Baseline characteristics of the patients' condition will be presented including the type of SOC (low molecular weight heparin, vitamin K antagonists, and fondaparinux), the type of leading index VTE, days since diagnosis of index VTE prior to randomization, characteristics of the index VTE, duration of parenteral anticoagulant treatment prior to randomization, and the types of initial parenteral anticoagulant therapy (unfractionated heparin, low molecular weight heparin, and etc.). The parenteral anticoagulant for initial treatment will also be listed. Other baseline characteristics including patients' baseline activated partial thromboplastin time (aPTT), Ecarin clotting time (ECT) among DE patients, and [international normalized ratio](#) (INR) and anti-factor Xa among SOC patients will be presented in an accompanying listing.

Descriptive statistics for demographics and baseline characteristics will also be presented by the subgroup of age stratum.

7.2 CONCOMITANT DISEASES AND MEDICATION

Concomitant diseases will be summarised descriptively. The concomitant medications taken at baseline and those taken while on treatment will be coded using the World Health Organization (WHO) Drug coding dictionary. These will then be summarized by WHO Drug ATC coding and listed by patient with each medication taken.

7.3 TREATMENT COMPLIANCE

Only descriptive statistics are planned for this section of the report. Average compliance of DE patients and SOC patients will be summarized and listed separately for the treated set. Number and percentage of patients with compliance categories <80%, 80%-120%, and >120% will also be presented.

7.4 PRIMARY ENDPOINTS

Primary analysis

The primary analysis of the primary efficacy endpoint will be performed on the randomized set following the intention-to-treat (ITT) principle, based on adjudicated data. For example: patients who were originally randomized to DE and later switched to SOC before Day 84, as cases of premature termination of the study medication, will be further followed up per the visit schedule until Day 84.

The analysis period in the primary analysis starts from the time of randomization to the time point of interest, that is, Day 84 \pm 7 days.

- For patients who die or withdraw consent prior to Day 84 – 7 days, the period for the primary analysis ends with the date of trial completion (i.e. the date of death, or the date of consent withdrawal).
- For patients who discontinue treatment prematurely (for example, due to complete thrombus resolution, AE, DE concentration out of target range after one dose modification, and so on), the latest available thrombus assessment up to Day 84 + 7 days will be used for the primary analysis. In particular, thrombus assessment performed after eEOT but before/at Visit 8 for patients switching from DE to SOC will be used for primary analysis. In terms of the recurrent VTE component or VTE-related mortality component, recurrence or death up to Day 84 + 7 days will be used for primary analysis.
- Patients who are still being treated and have not yet reached Day 84 \pm 7 days at time of EMA interim data cut-off will not be included in the analysis

The primary efficacy endpoint contains three components. Given the composite nature of the primary endpoint, each component will be evaluated separately, and a joint outcome of achieving the primary endpoint will be concluded only if all three components are satisfied.

Component 1: free from VTE-related mortality

Patients with VTE-related death occurring between randomization to Day 84 + 7 days will be considered as NOT meeting the endpoint in terms of the component of “freedom from mortality related to VTE”, and therefore will not contribute to the proportion of patients achieving the primary efficacy endpoint.

Component 2: free from recurrent VTE

The presence of recurrent VTE(s) will be examined throughout the study periods. Unscheduled visits would be conducted in case of suspected recurrence of VTE, so the risk of failure to detect recurrent VTE would be minimized. Patients with multiple recurrent VTEs will be regarded equally as patients with a single recurrent VTE, and only the date of first occurrence will be used for analysis.

Proprietary confidential information © 2019 Boehringer Ingelheim International GmbH or one or more of its affiliated companies

- For patients with recurrent VTE(s) from randomization to Day 84 + 7 days, the component of “free from recurrent VTE” will be considered as NOT satisfied.
- For patients WITHOUT ANY recurrent VTE records:
 - If the entire treatment period is completed (Visit 8 available), the component of “free from recurrent VTE” will be considered as satisfied.
 - If patients die (not VTE-related) or withdraw consent prior to Day 84 - 7 days, the period for VTE assessment ends with the date of trial termination (i.e. the date of death, or the date of consent withdrawal). In the primary analysis, we use last-observation-carried-forward (LOCF)², so no record of recurrent VTE will be considered as “free from recurrent VTE”.
 - If patients discontinue treatment prematurely due to reasons other than death or consent withdrawal, they are expected to be followed up for the remainder of planned study visits and will remain in the randomized set. The decision of whether achieving this efficacy endpoint component depends on the timing of their last study visit, if
 - Last study visit¹ took place on or after Day 84 + 7 days and there is no record of recurrent VTE ever, then the component of “free from recurrent VTE” will be considered as satisfied;
 - Last study visit took place before Day 84 + 7 days, then this component will be considered as missing. In the primary analysis, we use last-observation-carried-forward (LOCF)², so no record of recurrent VTE will be considered as “free from recurrent VTE”.
- Patients with VTE recurrence after Day 84 + 7 days will be considered as recurrent VTE free in the primary analysis,

1. Early discontinued patients should be followed up based on IIT principle, so the last study visit could be Visit 9 or further follow-up visit which is available and latest in time.

2. Given minimized risk of not detecting recurrent VTE due to the study design, as well as the low incidence rate of recurrent VTE in the study population, we assume patients free from recurrent VTE until the presence of contradictory evidence - observed VTE recurrence.

Component 3: complete thrombus resolution

Assessment of index VTE status (best overall response) is scheduled on Day 84 ± 7 days (Visit 8) for patients who are alive without an early consent withdraw, regardless of the treatment status (completion or premature discontinuation) at that time.

- The thrombus status assessed at Day 84 ± 7 days will be used for evaluation of this component. If more than one thrombus assessment is available within this time window, the one closest to Day 84 will be adopted. Furthermore, if two index assessments performed within the time window were equally distant from Day 84 (e.g., an early assessment on Day 78 and a late assessment on Day 90), then the thrombus status after Day 84 will be adopted.
- For patients completing the treatment period OR patients terminating treatment early, if the index thrombus assessment during Day 84 ± 7 days is missing, but an early VTE assessment was performed, for instance, at an unscheduled visit or an eEOT visit, the latest available thrombus status will be carried forward (LOCF) in the primary analysis.
- If not any index VTE assessment was performed until Day 84 + 7 days, these patients will be considered as having missing data and NOT meeting the criterion of “complete thrombus resolution”.
- Patients with index VTE assessment performed only once after Day 84 + 7 days will be considered to have missing data and to not achieve the complete thrombus resolution in the primary analysis,

Age group will be used as stratification factor using a Mantel-Haenszel type weighted average of differences with weights as proposed by Greenland and Robins [R09-1299] (3).

The testing hypotheses for the non-inferiority and superiority of the primary endpoint are:

$H_{01}: p_{IC} - p_{ID} \geq 20\%$ vs. $H_{11}: p_{IC} - p_{ID} < 20\%$, where p stands for the proportion of patients meeting the primary endpoint, the subscript C for SOC, and D for dabigatran etexilate.

$H_{03}: p_{IC} - p_{ID} \geq 0$ vs. $H_{13}: p_{IC} - p_{ID} < 0$.

The details of Cochran-Mantel-Haenszel test and SAS code are provided in [Section 9.4](#).

The non-inferiority of DE to SOC will be claimed if H_{01} were rejected. The superiority of DE will be claimed if H_{03} were rejected.

Upon showing non-inferiority for the primary endpoint, superiority test for the primary endpoint will be performed subsequently at one-sided level of 0.05 without multiplicity correction.

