6.2.3 End of trial and follow-up period

Patients who complete the treatment period and are not enrolled into the secondary VTE prevention study (BI trial 1160.108) are to be followed at Visit 9. For the schedule of assessments and procedures to be done at the follow-up visit refer to the [Flow Chart](#).

All patients who prematurely discontinue study medication will be invited to perform an eEOT Visit and the follow-up Visit 9, taking place 28 days thereafter. Subsequently they will be followed-up preferably according to the remaining visit schedule until the end of the

Proprietary confidential information.

© 2019 Boehringer Ingelheim International GmbH or one or more of its affiliated companies. All rights reserved.

This document may not - in full or in part - be passed on, reproduced, published or otherwise used without prior written permission.

study. At these visits collection of AEs, outcome events (e.g. occurrence of PTS, VTE, bleeding events, etc.) and use of concomitant medication will be done.

Patients having switched from dabigatran etexilate to SOC are considered as having early discontinuation of dabigatran etexilate treatment. However, such patients will still remain in the trial and will be followed as per the visit schedule till the end of the study. Patients having switched from one SOC to another during the treatment period, are not considered as having early discontinuation of treatment and should remain in the treatment period and be followed as per the visit schedule till the end of the study.

Proprietary confidential information.

© 2019 Boehringer Ingelheim International GmbH or one or more of its affiliated companies. All rights reserved.

This document may not - in full or in part - be passed on, reproduced, published or otherwise used without prior written permission.

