6. GENERAL ANALYSIS DEFINITIONS

6.1 TREATMENTS

There are two treatment arms in the study: DE using a dosing algorithm or SOC. The assignment of treatment groups will be based on randomization for randomized patient set as defined in [Section 6.3](#). Patients will be allocated to one of the following treatments given below.

Table 6.1: 1 Labels of treatments for use in the Clinical Trial Report

Treatment	Long label	Short label
A	Dabigatran etexilate	DE
B	Standard of care	SOC

Patients switching from DE to SOC before the end of study will be considered as having treatment periods defined below. Patients switching from the original SOC treatment to another SOC will be considered as no change in the treatment group assignment.

The following periods will be defined:

- Screening: day of informed consent to the day prior to first administration of the trial treatment (DE or SOC)
- On-treatment: day of first administration of trial treatment to last administration of trial treatment + 6 days (residual effect period). This on-treatment period will be used for analysis of safety endpoints and adverse events (AEs), as specified in [Section 7.8.1](#).
- Post-treatment: end of on-treatment period +1 day up to day of the last follow-up visit, lost to follow-up, death, or consent withdraw regarding participation in the trial.
- Post-study: For patients not rolled over to the 1160.108 trial, it starts from last follow-up visit + 1 day up to end of the trial, i.e. the last contact/information received during the trial. For patients rolled over to the 1160.108 trial, it starts from last follow-up visit + 1 day in 1160.106 to the date of informed consent in 1160.108.
- Intention to treat: day of randomization up to Day 84 (+ 7), including all observed time on and off trial medication.
- Full follow-up: day of randomization up to day of the last follow-up visit, lost to follow-up, death, or consent withdrawn regarding participation in the trial.

Please note: for patients who had not reached the end of a treatment period as defined above at EMA interim data cut-off date, the respective treatment period ends at the cut-off date.

The screening, on-treatment, post-treatment, and post-study periods will be used for the summary and listings of AEs. The intention to treat, on-treatment, and full follow-up periods will be used for descriptive and statistical analysis of primary/secondary/further endpoints.

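### At the EMA interim cut-off, whether a recent patient counts in the primary analysis depends on being still under treatment, a post-randomisation status that the SAP does not define

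*SAP*

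**What the plan says.** SAP 7.4 analyses the primary endpoint on the randomized set following ITT, from randomisation to Day 84 ± 7. Three bullets then deal with particular patients.

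- **Deaths and withdrawals.** "For patients who die or withdraw consent prior to Day 84" − 7 days, the analysis period ends at the date of death or withdrawal.
- **Early stoppers.** The latest thrombus assessment up to Day 84 + 7 is used. Under Component 2, "they are expected to be followed up for the remainder of planned study visits and will remain in the randomized set". With no recorded recurrence they count as recurrence-free. Under Component 3, with no index assessment they count as not resolved.
- **Cut-off.** The group concerned is "Patients who are still being treated and have not yet reached Day 84", allowing for the visit window of a week either side. Anyone in that position "at time of EMA interim data cut-off will not be included in the analysis".

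Only the third bullet excludes anyone, and it is the only one that mentions the cut-off. Elsewhere, SAP 6.1 says that for a patient whose analysis period is unfinished at the cut-off, "the respective treatment period ends at the cut-off date". SAP 7 states a general denominator rule: "Percentages will be based on all patients in the respective patient set whether they have non-missing values or not".

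**The concern.** ITT analysis of the randomized set should fix membership at randomisation. Here, among patients who have not reached Day 84, those still on treatment are held back and those who died, withdrew or stopped are counted. The stoppers are not finished cases either: their Day 84 assessment is still due, so they are scored on carried-forward or missing data.

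Stopping is not neutral. Protocol 3.3.4.1 ends treatment when imaging confirms complete resolution, which raises an arm's success rate. Stops for other reasons tend to lower it. Some compulsory stops apply only to dabigatran: a trough still out of range after one dose adjustment (Protocol 4.1.3), and confirmed events under Flow Chart footnote D.

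The rule also turns on a status that the SAP does not define. Two programmers could build different cut-off populations from the same data.

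**Working it through.** **1. Who is still being treated: two readings**

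- *Reading 1.* A switch from dabigatran (DE) to standard of care (SOC) counts as stopping. SAP 7.4 describes such switches "as cases of premature termination of the study medication", and Protocol 6.2.3 says "Patients having switched from dabigatran etexilate to SOC are considered as having early discontinuation of dabigatran etexilate treatment". A change from one SOC drug to another does not count (Protocol 4.1.4 and 6.2.3). Selection then depends on arm as well as course.
- *Reading 2.* A switcher on SOC is still on trial treatment. SAP 6.1 describes trial treatment as DE or SOC, and SAP 7.8.1 gives switchers a SOC on-treatment period. Most of the arm difference goes, but patients who stop all anticoagulation, for example after early resolution, are still selected in.

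Selection on a post-randomisation event remains under either reading.

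**2. The plan's own figure**

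Protocol 7.6 gives 82% power for 94 and 47 patients, 72% in both arms, a 20-point margin and a 90% confidence interval. Exact binomial enumeration of its unpooled bound (z = 1.64) gives 81.8%, so the figure reproduces. It does not bear on the cut-off rule; it only confirms the inputs.

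**3. Size of the selection**

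From the documents: 94:47 allocation, 72% success, and up to 15% early discontinuation on DE (Protocol 7.6).

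Assumed, because the documents give no cut-off date, accrual curve or SOC stopping rate:

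- Recent patients R. Even accrual of 141 over the 1,635 days from Amendment 1 (02 Oct 2014) to the revised TSAP (25 Mar 2019) gives 141 × 84/1635 = 7.24. If the limit is Day 77 or Day 91 it is 6.64 or 7.85. R = 20 and 40 represent late-loaded accrual.
- DE stopping 15%; half of eventual stops already seen at the cut-off.
- SOC stopping d = 0, 5% or 15%.
- Success e among stoppers from 0 to 1, against 0.72 otherwise.

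Formulas:

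- Stoppers added: k_DE = (2R/3) × 0.15 × 0.5; k_SOC = (R/3) × d × 0.5.
- Base (a), 141 in total including the recent patients: n_DE = 94 − 2R/3, n_SOC = 47 − R/3.
- Base (b), 141 already past the window and the recent patients on top (141 is a minimum): n_DE = 94, n_SOC = 47.
- Shift in each arm = k/(n + k) × (e − 0.72); net shift = DE − SOC.

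Example, (a), R = 20, d = 0, e = 0: k_DE = 13.33 × 0.075 = 1.00 and n_DE = 80.67, so the shift is 1/81.67 × (−0.72) = −0.88 points.

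Net shift in the DE − SOC difference, in points (e = 0 / e = 1):

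| Case | R = 7.24 (k_DE 0.36) | R = 20 (k_DE 1.00) | R = 40 (k_DE 2.00) |
|---|---|---|---|
| (a), d = 0 | −0.29 / +0.11 | −0.88 / +0.34 | −2.08 / +0.81 |
| (a), d = 5% | −0.19 / +0.08 | −0.59 / +0.23 | −1.37 / +0.53 |
| (a) or (b), d = 15% | 0 | 0 | 0 |
| (b), d = 0 | −0.28 / +0.11 | −0.76 / +0.29 | −1.50 / +0.58 |
| (a), Reading 2, d = 0, one third of DE stops end all treatment (assumed) | −0.10 / +0.04 | −0.30 / +0.12 | −0.71 / +0.27 |

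With the limit at Day 77 or Day 91, the even-accrual figures in (a) with d = 0 are −0.27 / +0.10 or −0.32 / +0.12.

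**4. Effect on power**

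For (b) with R = 20 and d = 0, using an unstratified normal approximation: SE = √(0.72 × 0.28 × (1/95 + 1/47)) = 0.0801, and power = Φ((0.20 + shift)/SE − 1.645). This gives 80.3% with no shift, 77.6% at −0.76 points and 81.3% at +0.29 points.

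**The case against.** Six points can be made for the plan.

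- **Inclusion of recent stoppers is inferred.** The first two bullets set periods and assessments; they are not written as cut-off eligibility rules. True, but the third bullet is the only exclusion shown, and it does not reach these patients.
- **The supporting text is general.** The denominator rule in SAP 7 concerns tables. The truncation note in SAP 6.1 covers everyone with an unfinished period, including those on treatment. Both are context only; the case rests on SAP 7.4.
- **The meaning is clear from contrast.** SAP 7.4 treats DE-to-SOC switchers as premature terminations, so Reading 1 is the natural one. That is fair, but Reading 1 is the reading under which selection also differs by arm.
- **Text may be missing.** SAP 9.4 is cited but not shown, and Table 6.3: 1 lists a sensitivity analysis on the treated set that the visible 7.4 does not describe. A definition there cannot be ruled out, though the cut-off bullet points to none.
- **The effect is tiny.** Under even accrual the rule adds about a third of one DE patient. Forty recent patients would be 28% of 141 in 5% of the assumed period, and no SOC stops is an extreme assumption. Some patients were also enrolled before Amendment 1, so the accrual clock is approximate. All of this stands and limits the size of the claim.
- **The remedy costs data.** It holds back patients already scanned at Day 77–90, and recent deaths, withdrawals and known failures. This also stands; the numbers are small.

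**Conclusion.** The concern holds. On its wording, the cut-off rule makes membership of an analysis described as ITT depend on events after randomisation that are related to outcome and, under the more natural reading, to arm. The deciding status is not defined in the text available.

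The expected bias is small against a 20-point margin: −0.3 to +0.1 points under even accrual, and −2.1 to +0.8 in the most late-loaded case examined with no SOC stops. It is zero if stopping and its outcomes are alike in the two arms. These ranges rest on assumed accrual, stopping rates and timing. The direction cannot be predicted. Only the cut-off analysis is affected, since the rule excludes nobody once all patients have passed Day 91. It merits correction because the defect lies in a stated rule, the trial is open-label, and the repair is simple.

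**What to change.** In SAP 7.4, replace the cut-off bullet with: *The cut-off analysis includes every patient randomised at least 91 days (84 + 7) before the cut-off, whatever the treatment status, and no one else.*

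This gives both arms the same rule, removes the selection under either reading, and settles whether the limit is Day 77, 84 or 91. The phrase about still being treated then needs no definition. The analyses of the endpoint's components in SAP 7.5.2 follow the primary analysis and should use the same population. The change should be made before the cut-off data are analysed.

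The cost is SAP wording, plus a few patients who wait for the final analysis: about 0.4 to 2 recent DE stoppers on the assumptions above, about one patient already scanned at Day 77–90 (141 × 14/1635 = 1.2 under even accrual), and any recent deaths or withdrawals, for which the documents give no rate.

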A discontinuation rate of up to 15% before the completion of at least 3 months treatment with dabigatran has been estimated for both 1160.106 and 1160.108 trials. 94 patients will be randomized to receive dabigatran in 1160.106 trial. It is estimated that there will be 120 patients entering 1160.108 by end of recruitment. Assuming that 20% of 1160.106 dabigatran patients will be rolled over to 1160.108, this would result in roughly 101 of the 120 total patients receiving dabigatran treatment in 1160.108 trial to be unique patients. Across both trials, this would result in $94 + 101 = 195$ unique patients treated with dabigatran. With a discontinuation rate of 15% (i.e. stop of treatment earlier than 3 months), a total of 166 unique patients are expected to complete at least 3 months of dabigatran treatment in both trials together.

Proprietary confidential information.

© 2019 Boehringer Ingelheim International GmbH or one or more of its affiliated companies. All rights reserved.

This document may not - in full or in part - be passed on, reproduced, published or otherwise used without prior written permission.

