7.5.2 Other secondary endpoints

Major bleeding events (MBEs)

MBEs will be analysed as time-to-event endpoint by Kaplan-Meier method using on-treatment analysis based on adjudicated data and treated set. The proportion of patients free from MBEs at the end of treatment period (84 days (Visit 8) or eEOT) will be provided by Kaplan-Meier estimates for the two treatment arms pooling all age groups. Due to the low event rate of major bleeding, age group stratification will not be considered. The confidence interval of proportion difference will be calculated based on Kaplan-Meier estimates and its variances.

Patients not having MBEs during the on-treatment period and patients who discontinue from the trial prematurely without having major bleeding events will be censored. For patients who have experienced more than one event during the trial, time to the first occurrence of the event will be used for analysis.

In case no MBE was observed in one of treatment arms, where the Kaplan-Meier estimate cannot be calculated, a descriptive table summarizing all MBEs will be provided.

PK/PD assessments

Analysis of standard PK/PD parameters will be performed according to 001-MCS-36-472_RD-01 on PKS, PDS, set as applicable (2).

Scheduled and unscheduled PK and PD data will be analysed separately. Only scheduled PK and PD data will be summarized descriptively. Unscheduled PK and PD data will be listed. As with unscheduled PK and PD data, PK and PD data collected at dose titration visits will be listed separately. The percentage of PK trough results (HPLC-MS/MS) within the target range of 50 to <250 ng/ml and outside target range at Visit 3, while at steady state (after at least six consecutive dabigatran etexilate doses), and following no more than one dose titration (again, at steady state (after at least 3 days following any dabigatran etexilate dose adjustment)) will be presented by formulation, by age group, and for patients treated with the capped dose and with the uncapped dose.

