Permanent discontinuation from therapy and the reasons will be summarized in the disposition table.

Assessment of acceptability

Assessment of acceptability of an age-appropriate formulation at the end of therapy will be provided descriptively for DE treated patients.

Assessment of acceptability of capsules, pellets and OLF reconstituted with flavoured or unflavoured solvent at Days 3 (Visit 3), 21 (Visit 5) and 84 (Visit 8), or eEOT after randomisation will be summarized descriptively as well. Questions completed by investigator, by parent/legal guardian, and by patients (if old enough per investigator judgement) will be summarized descriptively.

Thrombus progression

Frequency of patients free from thrombus progression at day 84 ± 7 days after randomization (or eEOT, whichever comes first) will be analyzed descriptively by treatment arm and age group. Patients without VTE assessments by this time point will be summarized as well. Mortality related to VTE will be considered as recurrence of VTE.

All bleeding events and all-cause mortality

All adjudicated bleeding events and adjudicated all-cause mortality will be analyzed as time-to-event endpoint using stratified Cox proportional hazard model with treatment as a covariate in the model and age group as the stratification factor. A pooling of age groups might be necessary if no events were observed in certain age group.

Patients that do not experience any bleeding events will be included as censored observations at the date of patients' last visit, the date of death not related to bleeding, or the date of data cut-off, whichever comes first. Patients being alive at the end of observational period will be censored for all-cause mortality at the date of patients' last date known to be alive, or the date of data cut-off whichever comes first. All bleeding events and all-cause mortality based on treated set will be analysed descriptively and by Kaplan-Meier estimates for each treatment arm.

Incidence of bleeding events including MBEs, CRNM, minor bleeding events, and any bleeding events will be presented, as well as incidence of combined endpoint of major and CRNM bleeding events.

Components of efficacy endpoint

All components of the primary endpoint will be analyzed as proportions using adjudicated data as the primary analysis in [Section 7.4](#). Concordance between adjudicated events and investigator-reported events will also be summarized.

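### The recurrent-VTE component scores children with truncated follow-up as recurrence-free, so the secondary proportion can only err upward; the error is probably small, and a time-to-event estimate beside it would show it.

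*SAP*

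**What the plan says.** SAP 7.4 gives the rules for Component 2. Two groups without a recorded recurrence matter here.

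- **Non-VTE death or consent withdrawal before Day 77 (Day 84 minus 7).** For these children "the period for VTE assessment ends with the date of trial termination". The last observation is carried forward, "so no record of recurrent VTE will be considered as" free from recurrence.
- **Early treatment stop for another reason.** The SAP states: "Last study visit took place before Day 84 + 7 days, then this component will be considered as missing". The same carry-forward then turns missing into free.

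Neither rule asks for a minimum length of follow-up. Footnote 2 gives the reason: detection failure is thought unlikely because of the study design, and incidence is thought low, so "we assume patients free from recurrent VTE until the presence of contradictory evidence - observed VTE recurrence". The design feature that Component 2 names is the unscheduled visit for suspected recurrence.

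SAP 5.2.2 lists the proportion free from recurrent VTE as a secondary endpoint. SAP 7.5.2 carries the scoring over: "All components of the primary endpoint will be analyzed as proportions using adjudicated data as the primary analysis in" Section 7.4. Protocol 7.3.2 likewise asks for the components as proportions under the primary model, which Protocol 7.3.1 defines as the age-stratified Mantel-Haenszel difference on the randomised set.

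Protocol 7.4 says missing data are in general not imputed. It names carry-forward only for thrombus resolution, and only if no VTE event fell between the two visits.

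**The concern.** The justification does not cover the whole endpoint. Recurrence is defined to include asymptomatic events and thrombus progression (Protocol 5.1.1, SAP 5.1). A silent event raises no suspicion and so triggers no unscheduled visit. The Flow Chart schedules assessment of thrombus extension only at Visit 1, Visit 8 and the early end-of-treatment (eEOT) visit, and a child whose follow-up is cut short may have neither of the last two. What is estimated is then the absence of a recorded recurrence while observed, not freedom from recurrence to Day 84.

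The SAP treats the same gap differently elsewhere. A child with no index-thrombus image by Day 91 fails Component 3 but can pass Component 2. Major bleeding is handled by Kaplan-Meier with censoring, and "The confidence interval of proportion difference will be calculated based on Kaplan-Meier estimates and its variances".

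At stake is the component a reader will check behind a composite driven mainly by thrombus resolution. If recurrence is understated, the reassurance it offers is slightly too strong. If follow-up is truncated more often in one arm and the unobserved risk is similar, the comparison leans toward that arm.

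**Working it through.** The plan gives no expected value, loss rate or power for this component, so there is no figure of its own to reproduce.

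**1. Who is affected.** Not every child whose last visit precedes Day 91. Under Protocol 6.2.3 a child who stops early has an eEOT visit, Visit 9 about 28 days later, then preferably the remaining schedule. For a stop before about Day 56 (84 - 28), the last visit is normally Visit 8, in the Day 77-91 window, with imaging. That child is labelled missing and scored free, but has been observed. The problem is confined to children whose follow-up ends before the Visit 8 assessment.

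**2. Direction.** In those children an unseen recurrence can only be scored as free:

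upward bias = f × r × u

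Here f is the share of the arm truncated, r their recurrence risk to Day 84, and u the share of that risk not observed. No term is negative. For non-VTE deaths, if death is treated as a competing event, only a silent recurrence before death is missed.

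**3. Inputs.**
- f: 5-15%, an assumption. The upper end borrows from Protocol 7.6: "A discontinuation rate of up to 15% before the completion of at least 3 months treatment with dabigatran has been estimated". That is stopping treatment, not loss to follow-up.
- r: 5.6% (2/36) and 10.0% (4/40), the 3-month recurrence-or-death figures of the earlier paediatric LMWH trial in Protocol 1.1, used as proxies.
- u: 0.5 if all recurrences are symptomatic, with events and losses spread evenly over Days 0-84; 1 if all are silent and found only at the Day 84 image.

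**4. Result, percentage points of upward bias per arm.**

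| f | r = 5.6%, u = 0.5 | r = 5.6%, u = 1 | r = 10%, u = 0.5 | r = 10%, u = 1 |
|---|---|---|---|---|
| 5% | 0.14 | 0.28 | 0.25 | 0.50 |
| 10% | 0.28 | 0.56 | 0.50 | 1.00 |
| 15% | 0.42 | 0.84 | 0.75 | 1.50 |

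At the largest entry, 0.15 × 0.10 × 1 = 0.015, so a true 90% would be reported as 91.5%. In an arm of 94 that is 94 × 0.15 × 0.10 = 1.4 recurrences unrecorded.

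**5. Between arms.** With equal true risk and equal u, the false difference is (difference in f) × r × u. For illustration, 15% against 5% with u = 1 gives 0.10 × 5.6% = 0.56 to 0.10 × 10% = 1.0 points. The documents give no loss rate by arm. They do make the eEOT visit required after any dabigatran dose but only if feasible under standard of care (Flow Chart, footnote E), so ascertainment could differ.

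**6. Scale.** One child is 1/94 = 1.1 points or 1/47 = 2.1 points. At 10% risk the half-width of a 90% interval for the difference is 1.645 × √[0.1 × 0.9 × (1/94 + 1/47)] = 8.8 points.

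**7. The composite.** A child with no index image by Day 91 already fails through Component 3. The remaining route is a child with complete resolution on an earlier image, such as at eEOT, who is then lost: both components carry forward as success.

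**The case against.** - **The inputs overstate the problem.** Children who stop treatment are to be followed (Protocol 3.3.4.1 and 6.2.3). Those who decline the schedule still get an eEOT visit and a contact at 4 months that asks about VTE. Full consent withdrawal is expected to be very rare. This largely stands, although a contact would not reveal a silent event.
- **The 10% may contain no recurrences.** In that arm of the earlier trial 4 of 40 had recurrence or death, and 4 died, all judged unrelated to VTE. This stands. Protocol 1.1 does not say whether silent recurrence was counted, so the true risk is simply not known.
- **The protocol prescribes proportions under the primary model.** Replacing them would depart from Protocol 7.3.2, drop age stratification and score one event by two rules. This stands, and is why the remedy should be an addition.
- **Censoring has its own assumptions.** Stopping for toxicity, out-of-range concentration or early resolution may be informative, and plain Kaplan-Meier ignores non-VTE death as a competing event. Both stand as limits on the remedy.
- **A time-to-event analysis may already be planned.** Component 2 says "only the date of first occurrence will be used for analysis". A reader might infer that the plan promises such an analysis and then omits it. The public text lacks SAP Sections 6.4, 7.6 and 9, so that inference is not safe.

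**Conclusion.** The point holds in a limited form. For children whose follow-up ends before the Visit 8 assessment, the rule counts unobserved time as recurrence-free, and the stated reason does not extend to asymptomatic events. The direction is fixed by the rule. The size is at most about 0.3 to 1.5 points per arm at 5-15% truncation and 5.6-10% risk with all of that risk unobserved, and half that if half is unobserved. These inputs are upper proxies that the documents do not establish, and the result is small beside an interval half-width of about 8.8 points.

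Two stronger readings are not supported. A reader might infer that the component is tilted toward dabigatran, but the documents give no truncation rate or unobserved risk by arm. A reader might also infer that the non-inferiority conclusion is at risk, but a child without an image already fails the composite, so little of the effect reaches it. This is a worthwhile minor improvement to a secondary endpoint on which no hypothesis is tested.

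**What to change.** Keep the age-stratified proportion, so that the component matches the composite and Protocol 7.3.2. In SAP 7.5.2 add, on the randomised set:

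- the cumulative incidence (or Kaplan-Meier estimate) of first adjudicated recurrent VTE at Day 84, counted from randomisation, with non-VTE death as a competing event;
- censoring at the last VTE assessment, stating whether that means imaging or clinical evaluation, because the Flow Chart schedules clinical evaluation at Visits 2 to 9 but imaging after baseline only at Visit 8 or eEOT;
- the Visit 8 assessment (Day 77-91) set to nominal Day 84;
- the between-arm difference with a confidence interval, as is already planned for major bleeding;
- the number of children by arm whose follow-up ended before the Visit 8 assessment.

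The cost is a few lines of SAP text and one extra table. The Flow Chart visits already supply the assessments needed. The drawbacks are a non-informative censoring assumption and a freedom rate that will look slightly less favourable.
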